##### **6.2.1 Concomitant therapy**

Prior medications are defined as drugs taken and stopped prior to the first dose of study medication.

Concomitant medication is defined as any medication, other than the Investigational Medicinal Product (IMP), which is given at least once between the day of first dose of study medication and the last day of study visit (including those which were started pre-baseline and continued into the treatment period or follow-up period), including prescription and over-the-counter medicines, and any traditional or herbal remedies.

Paracetamol as an antipyretic, and metopimazine for repeated vomiting (or if not available, any other antiemetic which is not known to prolong QT and/or cause torsade de pointes) will be allowed. If paracetamol or equivalent drug is given as an antipyretic up to 72 hours prior to the first dose, it has to be reported as prior medication.

Metoclopramide is contraindicated from the period prior to the first dose to Day 5 post-dose (120 hours).

Beta-lactam antibiotics can be given in case of a bacterial infection appearing after enrolment. All antibiotics, new-quinolones included, with anti-malarial activity should be prohibited.

The investigator must instruct the patient (or parent/legal guardian) to notify the study site about any new medications he/she takes after the patient was enrolled into the study. All medications, procedures and significant non-drug therapies (including physical therapy and blood

transfusions) administered after the patient was enrolled into the study must be recorded in the concomitant medications eCRF.

Each concomitant drug must be individually assessed against all exclusion criteria/prohibited medication. If in doubt the investigator should contact the Novartis medical monitor before randomizing a patient or before allowing a new medication to be started.

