### **PCT and FCT:**

Descriptive statistics (mean, standard error, median, quartiles) will be presented using the Kaplan-Meier method. Kaplan-Meier curves will be provided.

PCT will be calculated based on uncorrected parasite counts. Patients without parasite clearance for whatever reason will be censored at the time of last parasite assessment. Patients who were enrolled on the basis of history of fever and did not subsequently have a fever at pre-dose will not be included in the analysis of FCT. Patients without fever clearance for whatever reason will be censored at the time of last temperature assessment.

For Cohorts 1 and 2 pooled, the treatment difference between KAF156 and LUM-SDF and Coartem® will be evaluated at the 2-sided 5% significance level using a log-rank test stratified by cohort. For each cohort, the treatment difference between 2 treatment groups will be evaluated at the 2-sided 5% significance level using a log-rank test.

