2.7 Analysis of secondary efficacy objective(s)

2.7.1 Secondary efficacy endpoints

Secondary efficacy variables include:

1. PCR-corrected ACPR at Days 15, Day 29 (Run-in Cohort) and 43;
2. Uncorrected ACPR at Days 15, 29, and 43;
3. Proportion of patients with parasitaemia at 12, 24, and 48 hours after treatment;
4. Time to parasite clearance (PCT), defined as time from the first dose until the first total and continued disappearance of (*P. Falciparum*) asexual parasite forms which remained at least a further 48 hours;
5. Time to fever clearance (FCT), defined as time from the first dose until the first time the body temperature decreased below and remained below 37.5°C (axillary equivalent) for at least a further 24 hours;
6. Proportion of patients with early treatment failure (ETF);
7. Proportion of patients with late clinical failure (LCF);
8. Proportion of patients with late parasitological failure (LPF);
9. Incidence rate of recrudescence and new infection at Days 15, 29 and 43.

Analyses of ACPRs (PCR corrected or uncorrected) will be based on the FAS and PPS. Analyses of other secondary efficacy variables will be based on the FAS.

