2.7.2.4 Parasite clearance time (PCT) and fever clearance time (FCT)

Descriptive statistics (mean, standard error, median, quartiles) will be presented using the Kaplan-Meier method. Kaplan-Meier curves will be provided.

PCT will be calculated based on uncorrected asexual parasite counts. Patients without parasite clearance for whatever reason will be censored at the time of last parasite assessment. Patients who were enrolled on the basis of history of fever and did not subsequently have a fever at pre-dose will not be included in the analysis of FCT. Patients without fever clearance for whatever reason will be censored at the time of last temperature assessment. Patients who received any antimalarial medication (including rescue medication) before (parasite or fever) clearance will be censored at the first use of antimalarial medication. If the study medication is vomited in the same date as the use of antimalarial medication, the last vomiting time on the study medication date is imputed as time of antimalarial medication. Otherwise, the antimalarial medication time can be imputed using the middle day time (12:00). The between treatment difference will be evaluated exploratorily using a log-rank test separately by cohort and stratified by cohort for pooling Cohorts 1 and 2 if cohort 2 does not stop early; otherwise log-rank test will be performed for Cohorts 1 and 2 separately.

Additional analysis for FCT will be performed by excluding patients who took anti-pyretic drugs (ATC2 code as N02 or M01) prior to FCT.

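### The additional fever-clearance analysis drops children by whether they took an antipyretic before their own fever cleared, so it selects on the outcome; censoring at first use would avoid this (minor, supportive analysis only)

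*SAP*

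**What the plan says.** SAP 2.7.1 defines the outcome as "Time to fever clearance (FCT), defined as time from the first dose until the first time the body temperature decreased below and remained below" the fever threshold for at least a further 24 hours. SAP 2.7.2.4 analyses it by Kaplan-Meier. Children enrolled on history who "did not subsequently have a fever at pre-dose will not be included in the analysis of FCT". For the rest, "Patients without fever clearance for whatever reason will be censored at the time of last temperature assessment". Antipyretic users stay in this main analysis.

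The same section gives a rule for antimalarials: "Patients who received any antimalarial medication (including rescue medication) before (parasite or fever) clearance will be censored at the first use of antimalarial medication". It then states the comparison: "The between treatment difference will be evaluated exploratorily using a log-rank test separately by cohort", and stratified by cohort when Cohorts 1 and 2 are pooled. Protocol 12.5.1 says the pooled FCT difference "will be evaluated at the 2-sided 5% significance level using a log-rank test stratified by cohort". SAP 2.7.2 calls the secondary endpoints supportive, with no multiplicity adjustment.

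The section ends with the analysis at issue: "Additional analysis for FCT will be performed by excluding patients who took anti-pyretic drugs (ATC2 code as N02 or M01) prior to FCT". That sentence names no test. It does not say whether pre-dose use counts, or what happens to a child who took an antipyretic and never cleared.

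On antipyretic use, Protocol 6.2.1 allows "Paracetamol as an antipyretic, and metopimazine for repeated vomiting" and has antipyretics given up to 72 hours before the first dose reported as prior medication. Protocol 6.2.2 asks that paracetamol doses and times be recorded exactly. Protocol 6.4 states that the study is open label.

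**The concern.** Whether a child took an antipyretic before fever cleared depends on how long the fever lasted. A child febrile for 60 hours has far longer to receive one than a child febrile for 6 hours. The exclusion therefore acts on a post-randomisation event whose observation window ends at the outcome, and the retained children are weighted towards short fevers.

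The purpose is reasonable: antipyretics lower temperature and may blur the antimalarial effect on fever. A reader is therefore likely to take this analysis as the clean one. It could be the more distorted of the two, in a direction set by how antipyretics were used in each arm. Treatment is known at the site and the plan does nothing to equalise use, so the arms may differ.

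**Working it through.** **Plan's own figure.** The documents give no effect size, event count or power for FCT, so there is nothing to reproduce.

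**Inputs from the documents.** 220 children randomised 1:1, so 110 per arm (SAP 3.1.1); temperature every 6 hours until afebrile for 24 hours (Protocol Table 8-4); two-sided 5% log-rank test (Protocol 12.5.1).

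**Assumptions, not in the documents.** 70% febrile at pre-dose, giving 110 × 0.70 = 77 per arm; exponential times with a control median FCT of 24 h; first antipyretic use independent of clearance; no antipyretic effect on temperature; 20% to 60% of an arm excluded.

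**Closed form.** Let clearance have hazard L and first antipyretic use hazard A.

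- P(T > t and T < first use) = [L/(L + A)] × exp(−(L + A)t). Among retained children the clearance hazard is therefore L + A, not L.
- The fraction excluded is q = A/(L + A), so the retained hazard is L/(1 − q) and the retained median is the true median × (1 − q). With q = 50%, 24 h becomes 12 h.
- The retained hazard ratio is (L1 + A1)/(L0 + A0), with 1 = KAF156/LUM-SDF and 0 = Coartem. Above 1 means faster clearance on KAF156/LUM-SDF.
- No true difference: the ratio is (1 − q0)/(1 − q1). For 40% v 20% it is 0.60/0.80 = 0.75; for 50% v 30%, 0.50/0.70 = 0.71; for 60% v 40%, 0.40/0.60 = 0.67.
- True ratio 1.5 with equal antipyretic hazards: the ratio is 1.5 − 0.5 × q0. For q0 = 10%, 20%, 40% and 60% it is 1.45, 1.40, 1.30 and 1.20.

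**Simulation.** 2,000 trials per row, 77 per arm, 6-hourly readings, cut at 96 h, unstratified log-rank. The last three columns give the percentage of trials rejecting at two-sided 5%.

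| True HR | Excluded, control / KAF156 arm | Retained HR (closed form) | All febrile children | Exclusion | Censoring at first use |
|---|---|---|---|---|---|
| 1 | 40% / 40% | 1.00 | 4.4 | 5.0 | 5.6 |
| 1 | 40% / 20% | 0.75 | 5.2 | 30.4 | 5.5 |
| 1 | 50% / 30% | 0.71 | 5.0 | 34.6 | 5.2 |
| 1 | 60% / 40% | 0.67 | 5.1 | 40.2 | 6.2 |
| 1.5 | 20% / 14% | 1.40 | 69.6 | 47.1 | 62.2 |
| 1.5 | 40% / 31% | 1.30 | 69.0 | 25.0 | 51.2 |
| 1.5 | 60% / 50% | 1.20 | 69.2 | 11.5 | 36.8 |
| 1.5 | 50% / 22% | 0.96 | 69.6 | 5.5 | 40.8 |
| 1.5 | 30% / 40% | 1.75 | 68.0 | 76.0 | 57.8 |

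In rows 5 to 7 the antipyretic hazards are equal; the excluded fractions differ only because fever is shorter in the treated arm. In the last two rows the hazards differ. Setting L0 = 1, the first antipyretic hazards are 1 and 0.43, giving (1.5 + 0.43)/(1 + 1) = 0.96. Reversed, they give (1.5 + 1)/(1 + 0.43) = 1.75. A real effect is erased in one case and exaggerated in the other.

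**Boundary case.** If antipyretics are given only at or before the first dose and are unrelated to fever duration, exclusion does not bias the comparison. With no true difference and 60% v 40% excluded it rejects 5.6%. With a true ratio of 1.5 and 40% excluded in each arm, the average one-step log-rank estimate is 1.58 with and without exclusion. Only precision is lost (power 46% v 68%).

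**The case against.** **Limited reach.** This is one added analysis of a supportive endpoint. A reader might infer that the trial's FCT result, or even its efficacy conclusion, is compromised. The documents do not support that: the main FCT analysis retains antipyretic users, and the primary endpoint and the non-inferiority decision do not use this analysis. This stands, and it sets the severity.

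**No test is named.** The log-rank sentence comes before the added sentence, which may mean only a Kaplan-Meier summary. The rejection rates apply only if the test is run here too. The shift in median and hazard ratio does not depend on a test.

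**Use rates are unknown.** At 10% of controls excluded with equal antipyretic hazards, the ratio moves only from 1.50 to 1.45. With no true difference and equal use, false positives are not inflated. A reader might conclude that the analysis always shows false differences or always loses most of its power; neither follows. Nor is FCT necessarily biased short in both arms, as the boundary case shows. Children who neither took an antipyretic nor cleared also stay in, censored.

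**Censoring is not free of bias.** Antipyretics are given because of fever, so first use may predict the remaining fever. In a run where severity drove both fever duration and antipyretic use, and use differed by arm, censoring gave 7% to 15% false positives. Exclusion gave 20% to 47%. The strength of that link is assumed. The point stands as a caveat, but exclusion was still worse.

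**Partly covered already.** SAP 2.4.2 summarises concomitant medication by treatment and ATC class. It does not restrict this to use before fever clearance, which is the summary needed here.

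**Conclusion.** The added analysis selects on the outcome whenever antipyretics are given during the fever. It then shortens the estimated FCT and pulls a real difference towards no difference, even with equal antipyretic hazards. With unequal use it can create, mask or exaggerate a difference.

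Under the stated assumptions, a true ratio of 1.5 is estimated as 1.45 to 1.20 when 10% to 60% of controls are excluded with equal hazards. A null ratio becomes 0.75 to 0.67 when exclusion differs by 20 points. If the log-rank test is run on this analysis, null rejection is 30% to 40% in those unequal settings. Power falls from about 69% to 47%, 25% and 12% at 20%, 40% and 60% control exclusion. These figures illustrate the mechanism and do not predict this trial, because the documents give no antipyretic use rates. They also ignore the temperature-lowering effect of antipyretics, which bears on the main analysis and is a plausible motive for the extra one.

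Severity: minor.

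**What to change.** In SAP 2.7.2.4, replace the exclusion with a rule such as: *An additional, supportive analysis of FCT will censor at the first post-dose use of an antipyretic (ATC2 N02 or M01) before fever clearance.* This follows the antimalarial rule already in the section. Then:

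- State how pre-dose antipyretic use is treated.
- State how a missing antipyretic time is imputed. The section has such a rule for antimalarials (last vomiting time, or 12:00) but none for antipyretics.
- Tabulate antipyretic use before fever clearance by arm.
- State whether the log-rank test applies to this analysis.
- Note that censoring assumes use is unrelated to the remaining fever duration and may still be somewhat informative.

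The cost is SAP wording, one censoring rule, one imputation rule and one table. Paracetamol times are already to be recorded, so no new collection should be needed. Censoring also gives up some precision: power of 62%, 51% and 37% in the three equal-hazard rows, against about 69% with all febrile children.

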2.7.2.5 Time to event analysis for Recrudescence

Recrudescence is defined as appearance of asexual parasites after clearance of initial infection with a genotype identical to that of parasites present at baseline. Recrudescence must be confirmed by PCR analysis.

Incidence rates of recrudescence at Days 15, 29 and 43 will be estimated by the Kaplan-Meier method based on the subset of FAS patients who have clearance of initial infection by Day 7.

Time to event (recrudescence) will be calculated from the time of first study medication to the date of first event if a patient experiences the event and is censored at the first use of non-study antimalarial medication for purpose other than recrudescence or at the time of last parasite assessment otherwise. Undetermined treatment failures due to missing PCR data will be considered as censored at the time of treatment failure. The between treatment difference will be evaluated exploratorily using a log-rank test separately by cohort and stratified by cohort for Cohorts 1 and 2 pooled if cohort 2 does not stop early; otherwise for Cohorts 1 and 2 separately.

2.7.2.6 Time to event analysis for new infection

New infection is defined as appearance of asexual parasites after clearance of initial infection with a genotype different from those parasites present at baseline. New infection must be confirmed by PCR analysis.

Incidence rates of new infection at Days 15, 29 and 43 will be estimated by the Kaplan-Meier method based on the subset of FAS patients who have clearance of initial infection by Day 7.

Time to event (new infection) will be calculated from the time of first study medication to the date of first event if a patient experiences the event and is censored at the first use of non-study antimalarial medication for purpose other than new infection or at the time of last parasite assessment otherwise. Undetermined treatment failures due to missing PCR data will be considered as censored at the time of treatment failure. The between treatment difference will be evaluated exploratorily using a log-rank test separately by cohort and stratified by cohort for Cohorts 1 and 2 pooled if cohort 2 does not stop early; otherwise for Cohorts 1 and 2 separately.

2.7.2.7 Subgroup analysis for selected efficacy variables

PCR corrected/uncorrected ACPRs at Day 29, PCT, and FCT will be summarized descriptively by the following subgroups using pooled Cohort 1 and 2 if Cohort 2 does not stop early. If Cohort 2 stops early, then these subgroup analyses will be performed only in Cohort 1

- Age groups as per [section 2.3](#)
- Baseline Weight groups as per [section 2.3](#)
- Sex (male vs female)

2.8 Safety analyses

All safety analyses will be performed using the safety set. Safety data for each cohort will be summarized separately. If Cohort 2 does not stop early, then safety analyses will also be performed on Cohort 1 and 2 pooled together. If there exists a similar treatment regimen of KAF-LUM dose combination among the Run-in Cohort, Cohort 1 and Cohort 2, selected safety analysis may also be presented on pooled cohorts

2.8.1 Adverse events (AEs)

The number and percent of patients with treatment emergent adverse events will be presented. The treatment emergent adverse events (events started on or after the first dose of study medication or events present prior to the first dose of study medication but increased in severity based on preferred term on or after the first dose of study medication) will be summarized by primary System Organ Class (SOC) and Preferred Term (PT).

Adverse events will be summarized by presenting, for each treatment group, the number and percentage of patients having at least one AE, having an AE in each primary system organ class and having each individual AE (preferred term). Summaries will also be presented for AEs by severity (Toxicity grade) and for study treatment related AEs. If a patient reported more than one adverse event with the same preferred term, the adverse event with the greatest severity

will be presented. If a patient reported more than one adverse event within the same primary system organ class, the patient will be counted only once with the greatest severity at the system organ class level, where applicable.

The MedDRA version used for reporting the adverse events will be described in a footnote.

The most common adverse events reported ($\geq z$ % in any group for each preferred term in the table by SOC and PT) will be presented in the clinical study report by descending frequency according to its incidence in overall group starting from the most common event. Here threshold value z is set to 5 (%) but it may be updated following review of the dry run outputs.

Separate summaries will be provided for deaths, serious adverse events, severe malaria, other significant adverse events leading to treatment discontinuation and adverse events leading to dose adjustment.

Serious adverse events in screening phase will be flagged in data listing due to rare frequency.

Patients who experienced a grade 3 or grade 4 AE will be summarized.

2.8.1.1 For the legal requirements of ClinicalTrials.gov and EudraCT

Two required tables on treatment emergent adverse events which are not serious adverse events with an incidence greater than 5% and on treatment emergent serious adverse events and SAE suspected to be related to study treatment will be provided by system organ class and preferred term on the safety set.

If for a same patient, several consecutive AEs (irrespective of study treatment causality, seriousness and severity) occurred with the same SOC and PT:

- a single occurrence will be counted if there is ≤ 1 day gap between the end date of the preceding AE and the start date of the consecutive AE
- more than one occurrence will be counted if there is > 1 day gap between the end date of the preceding AE and the start date of the consecutive AE

For occurrence, the presence of at least one SAE / SAE suspected to be related to study treatment / non SAE has to be checked in a block e.g., among AE's in a ≤ 1 day gap block, if at least one SAE is occurring, then one occurrence is calculated for that SAE.

Number of deaths resulting from SAEs suspected to be related to study treatment and number of deaths resulting from SAEs irrespective of causality will be provided.

2.8.1.2 Subgroup analysis for AEs

The adverse events and SAEs will be summarized by the following subgroups using pooled Cohort 1 and 2 if Cohort 2 does not stop early. If Cohort 2 stops early, then these subgroup analyses will be performed only in Cohort 1.

- Age groups as per [section 2.3](#)
- Baseline Weight groups as per [section 2.3](#)
- Sex (male vs female)

Algorithms for date imputations is provided in Appendix 5.

2.8.1.3 Adverse events of special interest / grouping of AEs

The adverse events of special interest are defined in the Case retrieval Sheet (CRS) which is updated for each MEDDRA dictionary. The CRS data are stored in TMS.ECRS SAS dataset corresponding to a subset of eCRS SAS view for which the following filtering criteria are applied

- Drug code = KAF156

- the latest version of MedDRA at the time of final database lock.

- End date is null (this means this is the latest CRS version). Potential risks based on the current CRS are listed in [Table 2-1](#).

The number and percent of patients with these special AEs will be summarized. In addition, listings of related adverse events will be provided.

Newly occurring liver enzyme abnormalities and QTcF abnormalities will be summarized (see [Sections 2.8.2 and 2.8.3.1](#))

2.8.2 Laboratory data

Descriptive statistics will be generated for all clinical laboratory tests performed (actual values and changes from baseline) for three groups of laboratory tests (hematology, clinical chemistry and urinalysis) by laboratory test, visit and treatment group. Maximum change from baseline during study will also be reported. Change from baseline will only be summarized for patients with both baseline and post baseline values and will be calculated as:

$$\text{change from baseline} = \text{post baseline value} - \text{baseline value}$$

The following laboratory parameters will be analyzed for hematology test group: hemoglobin, platelets, white blood cell count, Reticulocytes, Haptoglobin, hematocrit, red blood cell (RBC) count, lymphocytes, lymphocytes (%), monocytes, monocytes (%), eosinophils eosinophils (%), neutrophils, neutrophils(%) , basophils, and basophils (%) .

The following laboratory parameters will be analyzed for Biochemistry test group: creatinine, total bilirubin (TBL), direct bilirubin, alanine aminotransferase (ALT), aspartate aminotransferase (AST), alkaline phosphatase (ALP), glucose, blood urea nitrogen (BUN). Sodium, potassium, calcium, creatinine, uric acid, gamma glutamyltransferase (GGT), magnesium, chloride, and total protein, albumin, INR, Thyroid Stimulating hormone (TSH), Thyroxine Free T4.

Change from baseline will only be analyzed for Hemoglobin, RBC, platelets, TBIL, ALT, AST.

Box plots for hematology and biochemistry parameters will be provided using normalized values, by dividing a value by its upper normal limit. Normalized values are used in the box plots since lab units and normal ranges could vary according to each site and also according to a certain age group. All lab values outside the normal ranges (High/Low) will be highlighted. The lab parameters without the normal reference ranges will be excluded from this plot.

Summary with frequency and percentage of patients with liver related events as defined in [Table 2-1](#) will be provided by treatment:

Table 2-1 Liver-related events

Parameter	Criterion
ALT	>3xULN; >5xULN; >8xULN; >10xULN; > 20xULN
AST	>3xULN; >5xULN; >8xULN >10xULN; >20xULN
ALT or AST	>3xULN; >5xULN; >8xULN >10xULN; >20xULN
ALT or AST and TBL	ALT or AST > 3 × ULN and TBL > 2 × ULN ALT or AST > 5 × ULN and TBL > 2 × ULN ALT or AST > 10 × ULN and TBL > 2 × ULN
TBL	>1.5xULN, >2xULN, >3xULN
ALP	>2xULN, >3xULN
ALP & TBL	ALP >3xULN & TBL >2xULN
(ALT or AST) & TBL & ALP	ALT or AST >3xULN & TBL >2xULN & ALP <2xULN

Listing of patients with the following renal related laboratories will be provided:

- Serum creatinine increase 25 – 49% compared to baseline
- Serum creatinine increase \geq 50% compared to baseline
- New dipstick proteinuria \geq 1+
- New dipstick hematuria \geq 1+

For urinalysis, frequency tables will be presented. Number and percent of patients in each category will be presented for each visit.

Laboratory measurements, which are recorded as below the lower limit of assay detection limits, will be imputed as half of the lower detection limit; and that above the upper limit of assay detection limit will be imputed as upper detection limit, for the summary statistics.

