**Table 8-5 Local laboratory evaluations**

Test Category	Test Name
Hematology	Hemoglobin, hematocrit (packed-cell volume - PCV), platelets, white blood cell (WBC) count with differential (as much as possible, neutrophil, lymphocyte and eosinophils counts will be performed while basophils and monocytes can be aggregated as 'other'). Red blood cell count (RBC), reticulocyte count and haptoglobin levels will be performed in case of significant hemoglobin drop > 2g/dL or hemoglobin levels ≤ 5g/dL (will be optional depending on site equipment).
Chemistry	
Routine blood chemistry testing will be performed according to the visit schedule in order to monitor the general medical condition of the patient.
 
This includes: Glucose, creatinine (serum), transaminases (ALT/Serum glutamic pyruvic transaminase (SGPT) and AST/Serum glutamic oxaloacetic transaminase (SGOT)), serum-γ-glutamyl transferase (GGT), Total and direct bilirubin, Alkaline Phosphatase (ALP), Blood Urea Nitrogen (BUN), prothrombin time International Normalized Ratio (INR), sodium, potassium, magnesium, calcium, chloride, total protein and albumin.
 
Thyroid stimulating hormone (TSH) and free thyroxine T4 are tested at screening, Day 15 and at study completion only.
 
At screening, results of the thyroid test are not mandatory for eligibility into the study.

Urinalysis	Dipstick measurements for specific gravity, protein, glucose and hematuria. Microscopy will be performed and urine sediment will be assessed in case of an abnormal dipstick test.

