## **Clinical laboratory evaluations:**

All laboratory data will be listed by cohort, treatment group, patient, and visit/time and if normal ranges are available abnormalities will be flagged. Summary statistics will be provided by cohort, treatment group, and visit/time. Shift tables using the low/normal/high/ (low and high) classification will be used to compare baseline to the worst post-treatment value.

[figure not shown]

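### SAP 2.8.2 omits the protocol's baseline-to-worst laboratory shift tables, gives maximum change no direction, contradicts itself on which tests get change from baseline, and only lists creatinine increases

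*SAP*

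**What the plan says.** Protocol 12.5.2, under clinical laboratory evaluations, plans summaries by cohort, treatment group and visit, and adds: "Shift tables using the low/normal/high/ (low and high) classification will be used to compare baseline to the worst post-treatment value".

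SAP 2.8.2 opens broadly: "Descriptive statistics will be generated for all clinical laboratory tests performed (actual values and changes from baseline) for three groups of laboratory tests", arranged "by laboratory test, visit and treatment group". It continues: "Maximum change from baseline during study will also be reported". It defines change as the post-baseline value less the baseline value, so a fall is negative. After naming the haematology and chemistry parameters it says: "Change from baseline will only be analyzed for Hemoglobin, RBC, platelets, TBIL, ALT, AST".

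For the liver, SAP Table 2-1 sets thresholds that are summarised as frequency and percentage by treatment. For the kidney the wording is "Listing of patients with the following renal related laboratories will be provided". That listing covers creatinine increases of 25-49% and of at least 50%, and new dipstick proteinuria or haematuria.

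Laboratory shift tables appear nowhere in the SAP. Section 4, which is for changes to the protocol's analyses, records none.

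**The concern.** Averages by visit show whether an arm moves as a whole. They do not show how many children had a clinically meaningful worst value at some point. That is the purpose of the protocol's shift table. It also classifies each value against its reference range, which matters here because SAP 2.8.2 itself notes that units and ranges vary by site and age group.

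Safety in children from 6 months of age is a stated secondary objective. According to the SAP introduction, the shells for the study report are prepared from the SAP. An output that the SAP does not name may therefore never be programmed. A maximum change with no stated direction may be programmed so that it reports recovery where the interest is in the fall.

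**Working it through.** The plan gives no figure to reproduce here. The check sets the passages side by side and adds short arithmetic.

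**1. Shift tables.** Protocol 12.5.2: planned, baseline to worst post-treatment value. SAP 2.8.2, Table 2-5 and 5.5: not mentioned. SAP Section 4: no change declared. The omission is therefore undeclared.

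**2. Which tests get change from baseline.** SAP 2.8.2 lists 17 haematology parameters and 21 chemistry entries. Creatinine appears twice, so there are 20 distinct chemistry parameters.

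- Total: 17 + 20 = 37.
- Allowed change from baseline by the later sentence: 6, and 6/37 = 16%.
- Allowed by the opening sentence: all of them.

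Both sentences cannot hold. The SAP's revision history records the six-test sentence as a June 2024 addition, so the opening sentence was probably left unadjusted. If the later sentence governs, creatinine, TSH and free T4 have no change from baseline, and no shift table either.

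**3. Direction of maximum change.** For total bilirubin, ALT and AST the harm is a rise. For haemoglobin, RBC and platelets, 3 of the 6 tests, it is mainly a fall. Take illustrative haemoglobin values of 11.0 g/dL at baseline, 8.5 on Day 8 and 11.8 on Day 43:

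- Day 8 change: 8.5 - 11.0 = -2.5.
- Day 43 change: 11.8 - 11.0 = +0.8.
- Signed maximum: +0.8. Minimum: -2.5. Largest absolute change: -2.5.

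The same effect at arm level was simulated on assumed inputs, with 200,000 patients per arm. There were five post-baseline visits (Days 2, 3, 8, 29 and 43). Mean changes were -0.3, -0.5, -0.4, +0.3 and +0.6 g/dL, with independent visit SD 0.7. One arm had an extra fall on Day 8 and half of it on Day 3. The table gives the difference between arms, affected minus other, in g/dL.

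| Extra Day 8 fall | Signed maximum | Minimum | Largest absolute | Day 8 change by visit |
|---|---|---|---|---|
| 1 | -0.04 | -0.63 | -1.09 | -1.00 |
| 2 | -0.04 | -1.47 | -2.29 | -2.00 |

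A signed maximum hides the transient fall. The minimum and the largest absolute change both show it. So does the by-visit change that the SAP already plans for haemoglobin, RBC and platelets.

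**4. Creatinine against liver.** Both have thresholds written into SAP 2.8.2. Liver results are counted by treatment; creatinine results are listed by patient. Table 2-5 follows the same pattern: liver, ECG and vital-sign abnormalities are marked for categorical summary, while the haematology and biochemistry rows are not.

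**5. Whether other text fills the gap.**

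- SAP 5.5 assigns CTCAE grades and refers to summaries by direction, but 2.8.2 and Table 2-5 name no such table.
- Table 5-7 selects the most extreme value for notable laboratory abnormalities, but the SAP gives no criteria for notable haematology, creatinine or thyroid values.
- Table 2-6 promises the DMC a categorical analysis of general laboratory tests without defining the categories.

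**The case against.** A reader might infer that falls in haemoglobin and platelets are misreported or missing by arm. The documents do not support that. Maximum change is an addition to summaries by visit and treatment group, and these three tests are among the six that keep change from baseline. In the example, the -2.5 enters the Day 8 summary of its arm. The default statistics in SAP 2.1 include the minimum, so the largest single fall at a visit is shown too.

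Nor does it follow that renal or thyroid findings are absent by arm. Actual creatinine, TSH and free T4 values are summarised by visit and treatment group. The box plots are scaled to the upper limit of normal, and out-of-range values, high or low, are to be highlighted. Laboratory abnormalities that qualify as adverse events are tabulated by arm. The wide age range does not confound the comparison either: safety is summarised by cohort, and randomisation is stratified by age group within Cohort 1.

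Two further replies carry some weight. SAP 2.1 points to protocol section 12 for the analysis, so the shift tables may still be intended. The signed reading of maximum change is also only one reading: for QTc the SAP says increase when it means increase, and a largest absolute change would capture the fall.

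These replies narrow the point without removing it. A general cross-reference does not specify a table, and an undefined statistic can be programmed either way.

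**Conclusion.** The point holds as a gap in specification. Four things need correcting:

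- a protocol-specified safety display is absent from the SAP and its absence is undeclared;
- two sentences conflict on whether change covers all listed tests or 6 of 37;
- maximum change has no direction, which matters for 3 of the 6 tests;
- creatinine categories are listed but not counted by arm.

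What is lost is each patient's worst value summarised by arm. By-arm reporting of these tests as a whole is not lost, and no efficacy conclusion is affected.

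The size of the direction problem depends on reading maximum as signed; on the largest-absolute reading it disappears for falls like the one shown. The simulation rests on assumed haemoglobin values and is illustrative only.

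The protocol also calls for extra haematology tests "in case of significant hemoglobin drop > 2g/dL or hemoglobin levels" at or below 5 g/dL. A reader might take the lack of a by-arm count of this flag as a further breach. It is not one: the flag triggers tests that are optional depending on site equipment, and the protocol's analysis section promises no such table.

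**What to change.** In SAP 2.8.2:

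1. Restore the low/normal/high shift tables from baseline to worst post-treatment value, by cohort and arm, for tests with a reference range, including creatinine, TSH and free T4. Otherwise, declare and justify the omission in Section 4.
2. Replace the undirected maximum change with a stated worst direction per test: minimum for haemoglobin, RBC and platelets; maximum for total bilirubin, ALT and AST.
3. Reconcile the opening sentence with the six-test sentence. If the restriction stays, say which displays cover the other tests.
4. Tabulate the creatinine categories already listed (25-49% and at least 50%) as n (%) by arm.

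A by-arm count of the protocol's haemoglobin flag is an optional addition.

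The cost is SAP wording and a few standard tables from data already collected. These are reporting changes only; no clinical threshold or action changes.
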